2.1.3 Secondary endpoint

The following pharmacokinetic parameters will be determined if feasible:

Part I and II

Single dose part (after the first dose):

- $AUC_{0-\infty}$ (area under the concentration-time curve of the analyte in plasma over the time interval from 0 extrapolated to infinity)
- C_{\max} (maximum measured concentration of the analyte in plasma)
- t_{\max} (time from dosing to maximum measured concentration of the analyte in plasma)

Part I only

After the last dose:

- $AUC_{\tau,ss}$ (area under the concentration-time curve of the analyte in plasma at steady state over a uniform dosing interval τ)
- $C_{\max,ss}$ (maximum measured concentration of the analyte in plasma at steady state over a uniform dosing interval τ)
- $C_{\min,ss}$ (minimum concentration of the analyte in plasma at steady state over a uniform dosing interval τ)
- $R_{A,C_{\max}}$ (accumulation ratio based on $C_{\max,ss}$)

Proprietary confidential information © 2021 Boehringer Ingelheim International GmbH or one or more of its affiliated companies

[figure not shown]
- $R_{A,AUC}$ (accumulation ratio based on $AUC_{0-\tau}$)

2.2.2.1 Safety and tolerability (Part I and II)

[figure not shown]
Safety and tolerability of BI 706321 will be assessed based on:

- AEs (including clinically relevant findings from the physical examination)
- Safety laboratory tests
- 12-lead ECG
- Vital signs (blood pressure, pulse rate, body temperature)

[figure not shown]
Proprietary confidential information © 2021 Boehringer Ingelheim International GmbH or one or more of its affiliated companies

[figure not shown]
Proprietary confidential information © 2021 Boehringer Ingelheim International GmbH or one or more of its affiliated companies

Proprietary confidential information © 2021 Boehringer Ingelheim International GmbH or one or more of its affiliated companies

Proprietary confidential information © 2021 Boehringer Ingelheim International GmbH or one or more of its affiliated companies

3. DESCRIPTION OF DESIGN AND TRIAL POPULATION

3.1 OVERALL TRIAL DESIGN AND PLAN

Part I:

This multiple-rising dose trial is designed as double-blind, randomised, and placebo-controlled within parallel dose groups.

It is planned to include a total of 48 healthy Japanese male subjects in the trial. The subjects will be assigned to 4 groups consisting of 12 subjects per group; the groups will be dosed sequentially (see Table 3.1: 1). Within each dose group, 9 subjects will receive BI 706321 and 3 will receive placebo. Only one dose is tested within each dose group.

The trial schedule and design are depicted in Figure 3.1: 1 below.

[figure not shown]

Figure 3.1: 1

Trial design "Part I"

The dose groups to be evaluated are outlined in Table 3.1: 1 below.

Table 3.1: 1 Dose groups

Dose Group	1	2	3	4
Daily dose (mg)	2	5	8	10
Number of subjects	12	12	12	12
Subjects receiving placebo	3	3	3	3
Subjects receiving BI 706321	9	9	9	9

The groups will be dosed consecutively in ascending order, and a time interval of at least 7 days will be maintained between the last drug administration to subjects in the previous dose group and the first drug administration to subjects in the subsequent dose group. The decision to treat the next dose group will be based upon safety and tolerability data of all the preceding dose groups. The next dose group will only be treated if, in the opinion of the investigator, no safety concerns have arisen in the preceding dose groups (i.e. no dose-limiting events occurred), and if none of the pre-specified trial-specific stopping criteria have been met (refer to Section 3.3.4.3).

Proprietary confidential information © 2021 Boehringer Ingelheim International GmbH or one or more of its affiliated companies

A documented safety review must take place prior to each dose escalation. Furthermore, an unscheduled safety review meeting can be requested anytime by the Principal Investigator (or an authorised deputy) or the sponsor of the study (for instance, due to the occurrence of any unforeseen adverse events).

Although no formal Safety Review meeting will take place within a given dose group, safety will be continuously monitored during this trial, and an individual will only be dosed in the absence of any safety concern (i.e. no dose-limiting events occurred) and if none of the pre-specified trial-specific stopping criteria have been met (refer to Section [3.3.4.3](#)).

At minimum, data from 7 subjects on active drug need to be available for escalation to a higher dose. The minimum data set for review consists of the following:

- AEs in the current and preceding dose groups up to at least 48 h post dosing, including clinically relevant findings from ancillary safety testing listed below (Note: AEs may be ongoing at the time of Safety Reviews and AE information may be subject to change prior to Database Lock)
- Results from 12-lead ECG in the current and preceding dose groups up to at least 48-hour post dosing
- Vital signs in the current and preceding dose groups up to at least 48-hour post dosing
- Clinical laboratory tests in the current and preceding dose groups up to at least 48-hour post dosing
- Check of criteria for stopping subject treatment as per Section [3.3.4.1](#)

The decision to escalate the dose will be made jointly by the Principal Investigator (or an authorised deputy) and the Clinical Trial Leader (CTL) (or an authorised deputy) after in-depth analysis of all available safety data, especially SAEs (if occurred), AEs, and out-of-range laboratory results (if considered clinically significant). In addition and depending on the results and findings, suitable experts from the sponsor or external institutions may be consulted on an as needed basis. In these cases, expert recommendations will be documented in the minutes of the Safety Review and considered for the decision making. Dose escalation will only be permitted if no safety concerns exist neither in the opinion of the Principal Investigator (or an authorised deputy) nor the Clinical Trial Leader (or an authorised deputy).

Safety Reviews can be conducted face-to-face or by video/telephone conference. The Clinical Trial Leader is responsible for the organisation and minutes of the reviews. Minutes will be signed off by the Principal Investigator (or an authorised deputy) and Clinical Trial Leader (or an authorised deputy), and will be filed in the ISF and TMF.

An overview of all relevant trial activities is provided in the [Flow Chart](#). For visit schedules and details of trial procedures at selected visits, refer to Sections [6.1](#) and [6.2](#), respectively.

Part II:

This single dose trial is designed as double-blind, randomised, and placebo-controlled

It is planned to include a total of 12 healthy Chinese male subjects in the trial. 9 subjects will receive BI 706321 and 3 will receive placebo. Only 10 mg dose is tested.

The trial schedule and design are depicted in Figure 3.1: 2 below.

[figure not shown]

Figure 3.1: 2 Trial design “Part I and II”

The group will be dosed only after all dose groups in Part I have been completed and if, in the opinion of the investigator, no safety concerns have arisen in the preceding dose groups in Part I (i.e. no dose-limiting events occurred), and if none of the pre-specified trial-specific stopping criteria have been met (refer to Section [3.3.4.3](#)).

3.2 DISCUSSION OF TRIAL DESIGN, INCLUDING THE CHOICE OF CONTROL GROUP

Part I:

For multiple-rising dose trials, the sequential rising dose design described in section 3.1 is viewed favourably under the provision not to expose the subjects involved to undue risks.

Double-blind conditions regarding the subject's treatment (active or placebo) are maintained within each dose group. However, subjects and investigators will be aware of the dose of drug administered. The disadvantage of the trial design is a possible observer bias with regard to the dose-dependent effects; in addition, the sequential dosing of groups could potentially result in time-related effects. However, as such effects are expected to be small relative to the differences between the doses in the broad range investigated, unbiased comparisons between treatments can still be expected.

It is standard in multiple rising dose trials involving healthy volunteers to include a placebo group to control for safety and tolerability of the trial medication. Each dose group consists of 12 subjects, with 9 on active treatment, and 3 on placebo. For data analysis purposes, the placebo control group will include all subjects of all dose groups treated with placebo. Nine subjects per active treatment group are generally considered to be sufficient for the exploratory evaluation of safety, tolerability and pharmacokinetics.

After the first dose (single dose part), a sufficient wash-out period will be included before the second dose (first dose of the multiple dose part) is administered. This will allow for appropriate calculation of pharmacokinetic parameters after a single dose administration and for comparison with pharmacokinetic parameters at steady state.

Part II:

For single dose trial, the dose designed described in section [3.1](#) is viewed favourably under the provision not to expose the subjects involved to undue risks.

Double-blind conditions regarding the subject's treatment (active or placebo) are maintained within the dose group. However, subjects and investigators will be aware of the dose of drug administered.

It is standard in single dose trials involving healthy volunteers to include a placebo group to control for safety and tolerability of the trial medication. The dose group consists of 12 subjects, with 9 on active treatment, and 3 on placebo. For data analysis purposes, the placebo control group will include all subjects of all dose groups treated with placebo. Nine subjects per active treatment group are generally considered to be sufficient for the exploratory evaluation of safety, tolerability, and pharmacokinetics.

3.3 SELECTION OF TRIAL POPULATION

Part I:

It is planned that *48 healthy* Japanese male subjects will enter the study. *Subjects will be recruited from the volunteers' pool of the trial site.*

Part II:

It is planned that *12 healthy* Chinese male subjects will enter the study. *Subjects will be recruited from the volunteers' pool of the trial site.*

Only male subjects will be included in the trial*.

A log of all subjects enrolled into the trial (i.e. who have signed informed consent) will be maintained in the ISF irrespective of whether they have been treated with investigational drug or not.

* Only male subjects will be enrolled in the study as standard for phase I trials in Japan. Although the pre-clinical data for BI 706321 does not mandate contraception requirements for males, these will be maintained for this study as part of standard precautions for phase I trials in Japan.

3.3.1 Main diagnosis for trial entry

The study will be performed in healthy subjects.

3.3.2 Inclusion criteria

1. Healthy male subjects according to the assessment of the investigator, as based on a complete medical history including a physical examination, vital signs (blood pressure [BP], PR including body temperature, 12-lead ECG, and clinical laboratory tests at screening visit
2. Part I:
Japanese ethnicity, according to the following criteria:
 - born in Japan, have lived outside of Japan <10 years,

Proprietary confidential information © 2021 Boehringer Ingelheim International GmbH or one or more of its affiliated companies

- have parents and grandparents who are Japanese

Part II:

Chinese ethnicity including Taiwanese, according to the following criteria:

- have parents and grandparents who are Chinese

3. Age of 20 to 45 years (inclusive) at screening visit
4. Body mass index (BMI) of 18.5 to 25.0kg/m² (inclusive) at screening visit
5. Signed and dated written informed consent prior to admission to the study, in accordance with Good Clinical Practice (GCP) and local legislation
6. Willingness to comply with contraception requirements. Subjects who are sexually active must use adequate contraception methods throughout the trial and until three months after the last administration of trial medication. Adequate methods are:
 - A vasectomy performed at least 1 year prior to screening and with medical assessment of the surgical success or
 - Surgical sterilisation, including bilateral tubal occlusion, hysterectomy or bilateral oophorectomy, of the subject's female partner or
 - The use of condoms, if the female partner uses an adequate contraception method in addition, e.g., intrauterine device (IUD), or hormonal contraception, such as implants and injectables*, combined with oral or vaginal contraceptives, that started at least 2 months prior to first drug administration, or barrier method, e.g., diaphragm with spermicide*

* hormonal contraception via implants and injectables, and diaphragm with spermicide are not approved in Japan

Unprotected sexual intercourse with a pregnant partner is not allowed throughout the trial and until three months after the last administration of trial medication.

3.3.3 Exclusion criteria

Subjects will not be allowed to participate, if any of the following general criteria apply:

1. Any finding in the medical examination (including BP, PR, body temperature or ECG) deviating from normal and assessed as clinically relevant by the investigator at screening visit
2. Repeated measurement of systolic blood pressure outside the range of 90 to 140 mmHg, diastolic blood pressure outside the range of 40 to 90 mmHg, or pulse rate outside the range of 40 to 99 bpm at screening visit
3. Any laboratory value outside the reference range that the investigator considers to be of clinical relevance at screening visit
4. Any evidence of a concomitant disease assessed as clinically relevant by the investigator
5. Gastrointestinal, hepatic, renal, respiratory, cardiovascular, metabolic, immunological or hormonal disorders
6. Cholecystectomy or other surgery of the gastrointestinal tract that could interfere with the pharmacokinetics of the trial medication (except appendectomy or simple hernia repair)
7. Diseases of the central nervous system (including but not limited to any kind of seizures or stroke), and other relevant neurological or psychiatric disorders, per investigator judgement
8. History of relevant orthostatic hypotension, fainting spells, or blackouts

Proprietary confidential information © 2021 Boehringer Ingelheim International GmbH or one or more of its affiliated companies

9. Chronic or relevant acute infections
10. History of relevant allergy or hypersensitivity (including allergy to the trial medication or its excipients)
11. Use of drugs within 30 days of planned administration of trial medication that might reasonably influence the results of the trial (including drugs that cause QT/QTc interval prolongation)
12. Intake of an investigational drug in another clinical trial within 30 days (or 5 half-lives (whichever longer)) of planned administration of investigational drug in the current trial, or concurrent participation in another clinical trial in which investigational drug is administered
13. Smoker (more than 10 cigarettes or 3 cigars or 3 pipes per day)
14. Inability to refrain from smoking on specified trial days
15. Alcohol abuse (consumption of more than 30 g per day for males)
16. Drug abuse or positive drug screening
17. Blood donation of more than 400 mL within 12 weeks or 200mL within 30 days or plasma donation within 2 weeks prior to administration or intended blood donation during the trial.
18. Intention to perform excessive physical activities within one week prior to the administration of trial medication or during the trial
19. Inability to comply with the dietary regimen of the trial site
20. A marked prolongation of QT/QTc interval (such as QTc intervals that are repeatedly greater than 450 ms) or any other relevant ECG finding at screening visit
21. A history of additional risk factors for *Torsade de Pointes* (such as heart failure, hypokalaemia, or family history of Long QT Syndrome)
22. Subject is assessed as unsuitable for inclusion by the investigator, for instance, because the subject is not considered able to understand and comply with study requirements, or has a condition that would not allow safe participation in the study
23. ALT (alanine transaminase) or AST exceed upper limit of normal range at screening visit, confirmed by a repeat test
24. Hb <13.0 mg/dL and platelets and neutrophils below lower limit of normal range at screening, confirmed by a repeat test
25. Positive result for HIV, HBV, HCV, and Syphilis infection at screening.
26. History of Tuberculosis (TB) or positive finding in IGRA.
27. A positive test result for SARS-CoV-2/COVID-19 (nucleic acid amplification methods) or clinical symptoms suggestive for this disease at the test prior to admission to trial site (i.e. Day -3 to Day -1).

For study restrictions, refer to Section [4.2.2](#).

3.3.4 Withdrawal of subjects from treatment or assessments

Subjects may discontinue trial treatment or withdraw consent to trial participation as a whole ('withdrawal of consent') ; please see sections [3.3.4.1](#) and [3.3.4.2](#) below.

If a subject is removed from or withdraws from the trial prior to the first administration of trial medication, the data of this subject will not be entered in the case report form (CRF) and will not be reported in the clinical trial report (CTR). If a subject is removed from or

Proprietary confidential information © 2021 Boehringer Ingelheim International GmbH or one or more of its affiliated companies

withdraws from the trial after the first administration of trial medication, this will be documented and the reason for discontinuation must be recorded in the CRF; in addition, the data will be included in the CRF and will be reported in the CTR.

At the time of discontinuation, a complete end of trial examination will be performed, if possible, and the information will be recorded in the CRF. If the discontinuation occurs before the end of the REP (see Section [1.2.2](#)), the discontinued subject should if possible be questioned for AEs and concomitant therapies at or after the end of the REP in order to ensure collection of AEs and concomitant therapies throughout the REP, if not contrary to any consent withdrawal of the subject.

Since the risks of drug exposure of a pregnant partner of a study participant via the seminal fluid are yet unknown, adequate contraception as outlined in Section [3.3.2](#), is a prerequisite for participation in the study and is still necessary even if the subject withdraws consent or is removed from the trial.

3.3.4.1 Discontinuation of trial treatment

An individual subject will discontinue trial treatment if:

1. The subject wants to discontinue trial treatment, without the need to justify the decision
2. The subject has repeatedly shown to be non-compliant with important trial procedures and, in the opinion of both, the investigator and sponsor representative, is not willing or able to adhere to the trial requirements in the future
3. The subject needs to take concomitant medication that interferes with the investigational medicinal product or other trial treatment
4. The subject can no longer participate this trial for medical reasons (such as surgery, adverse events [AEs], or diseases)
5. An AE or clinically significant laboratory change or abnormality occurs that the investigator assesses as warranting discontinuation of treatment. This may include cases of:
 - sustained symptomatic hypotension (BP <90/50 mmHg) or hypertension (BP >180/100 mmHg),
 - clinically relevant changes in ECG requiring intervention,
 - moderate to severe acute infection,
 - fever lasting longer than 24 hours, or
 - unexplained clinically relevant hepatic enzyme or CRP elevation, or decrease in red blood cell count, reticulocytes, or thrombocytes at any time during the trial. These respective laboratory tests need to be closely monitored and drug administration continued only if in the opinion of the investigator it is safe to do so.
6. The subject has an elevation of AST and/or ALT \geq 3-fold upper limit of normal (ULN) and an elevation of total bilirubin \geq 2-fold ULN (measured in the same blood sample) and/or needs to be followed up according to the DILI checklist provided in the ISF

In addition to these criteria, the investigator may discontinue subjects at any time based on his or her clinical judgment.

Proprietary confidential information © 2021 Boehringer Ingelheim International GmbH or one or more of its affiliated companies

Even if the treatment is discontinued, the subject remains in the trial and, given his agreement, will undergo the procedures for early treatment discontinuation and follow up as outlined in the [Flow Chart](#) and section [6.2.3](#).

3.3.4.2 Withdrawal of consent to trial participation

Subjects may withdraw their consent to trial participation at any time without the need to justify the decision. If a subject wants to withdraw consent, the investigator should be involved in the discussion with the subject and explain the difference between trial treatment discontinuation and withdrawal of consent to trial participation, as well as explain the options for continued follow up after trial treatment discontinuation, please see Section [3.3.4.1](#) above

3.3.4.3 Discontinuation of the trial by the sponsor

Boehringer Ingelheim reserves the right to discontinue the trial at any time for any of the following reasons:

1. Failure to meet expected enrolment goals
2. New toxicological findings, serious adverse events, or any safety information invalidating the earlier positive benefit-risk assessment.
3. Violation of GCP, or the clinical trial protocol (CTP), or the contract with BI impairing the appropriate conduct of the trial.
4. The sponsor decides to discontinue the further development of the investigational product
5. Dose escalation will be stopped if at least 2 subjects on active treatment at one dose level have relevant individual QT prolongations, i.e. a QTc increase of greater than 60 ms from baseline in connection with absolute QT or QTc greater than 500 ms, as confirmed by a repeat ECG recording

The investigator / trial site will be reimbursed for reasonable expenses incurred in case of trial termination (except if item 3 applies).

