5. AEs and concomitant therapies will be recorded throughout the trial, but will be specifically asked for at the times indicated in the [Flow Chart](#) above.
6. On all non-intensive PK days, standard light breakfast will be served approx. 1 hour after the dose. On all study days standard meals (lunch and dinner) will be given approx. 4 and 10 hours post dose.
7. The ECG recording has to be performed in triplicate at this time.
8. Sampling times and periods may be adapted based on information obtained during the trial including addition of samples and visits as long as the total blood volume drawn does not exceed 400 mL per subject.

Proprietary confidential information © 2021 Boehringer Ingelheim International GmbH or one or more of its affiliated companies

9. A blank urine sample (x) is to be obtained prior to administration of trial medication. Other urine samples are to be collected over the stated post-dose intervals (◀—|—|→) 0-4, 4-8, 8-12, 12-24, 24-48, 48-72, 72-96 and 96-120 h on days 1 and 19 for all doses. For 2 mg dose group, samples over the post-dose interval 96-120 h are not to be collected (samples over the post-dose interval 0-4, 4-8, 8-12, 12-24, 24-48, 48-72, 72-96 are to be collected). On day 12, the samples are to be collected over the stated post-dose intervals (◀—|—|→) 0-4, 4-8, 8-12, 12-24 h for all dose groups.
10. At baseline (i.e. Day 1, prior to drug administration) and Day 19, 3 triplicate ECGs are recorded within approximately one hour. The recordings should be separated by at least 15 minutes.
11. This is nominal time. Actual visit procedures may be performed anytime between day -3 and day -1.
12. The hospitalization may be extended for operational reasons.
13. SARS-CoV-2/ COVID-19 test (nucleic acid amplification methods) as well as body temperature assessment will be performed once prior to admission to trial site during the period from Day -3 to Day -1, at the end of trial visit unless subject is hospitalized throughout the trial, and when the infection is suspected during the trial.
14. Safety laboratory to be taken and to be medically evaluated within 3 days prior to administration of study drug; this repeat safety laboratory can be omitted, if the screening examination is performed on Days -3, -2 or -1.

Proprietary confidential information © 2021 Boehringer Ingelheim International GmbH or one or more of its affiliated companies

Part II:

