In rats, repeat dosing up to 13 weeks duration resulted in increased incidence/severity of mononuclear infiltrates. Infiltrates were associated with an increased incidence of myocardial degeneration at higher exposure levels (84X/60X Cmax and AUC respectively). The finding in rats may be a species-specific exacerbation of a common spontaneous background finding in rats. No histopathologic changes to the heart were seen in long term toxicology studies in monkeys. There is low risk for relevant cardiovascular effects to subjects at the clinically relevant short-term exposures planned in this trial. For safety margins between maximum exposure in this trial and findings in the Good Laboratory Practice (GLP) cardiovascular findings in rats refer to the current version of the IB. Studies in monkeys showed potential for prolongation of QT/QTc intervals. In the MRD trial, an exploratory analysis of central ECG data was conducted to characterise the effects of BI 706321 on QT/QTc. Based on preliminary analysis using random coefficient modelling, the predicted mean differences between BI 706321 and placebo in QTcF change from baseline at gMean of $C_{max,ss}$ were below 10 msec at all dose levels; however, they slightly exceeded 5 msec in the 8 and 10 mg dose groups. No clinically relevant individual QTcF

Proprietary confidential information © 2021 Boehringer Ingelheim International GmbH or one or more of its affiliated companies

changes have been observed in any subject exposed to BI 706321; no relevant blood pressure or heart rate changes were noted.

Risk mitigation:

Subjects with relevant findings in BP, PR or ECG at Screening, cardiovascular disorders, history of relevant orthostatic hypotension, fainting spells or blackouts, use of drugs that might prolong the QT/QTc interval, marked ([Section 3.3.3](#)), or subjects with additional risk factors for Torsade de Pointes arrhythmia ([Section 3.3.3](#)) are excluded from trial participation.

- A dose escalation stopping criterion based on QT/QTc increase has been defined ([Section 3.3.4.3](#)).
- Frequent ECG and vital signs measurements during the time of expected relevant exposure (see [Flow Chart](#)).

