4.1.5 Blinding and procedures for unblinding

4.1.5.1 Blinding

The trial is designed double-blind. The treatments administered (active or placebo) will be blinded to the subjects and the investigators (outcome assessors) in order to limit the occurrence of any bias which the knowledge of treatment may have.

Regarding the sponsor, all trial data will be handled open label. This means that trial functions of the sponsor are unblinded (including Clinical Trial Leader, data manager, statistician, bioanalyst, pharmacokineticist, pharmacometrist, drug metabolism scientist as well as dedicated contract research organization (CRO) personnel). The objective of the trial is not expected to be affected.

The randomization schedule will be access controlled until the randomization has completed.

The trial site will only be unblinded after locking of the database.

Within the central ECG lab, the staff involved with interval measurements and assessments will be blinded with respect to the treatment and also with regard to the recording date and time as well as planned time points of the ECGs. The interval measurements for a given subject will be performed in a random and blinded sequence by a single technician. No more than two different blinded readers will evaluate the ECGs of the trial.

If an interim safety analysis of ECG data is required, a part of the staff of the central ECG lab may be unblinded. This part of the staff will be strictly separated from the blinded staff members who are involved with ECG interval measurements and assessments of ECGs.

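### In Part I, no scheduled ECG near peak concentration at accumulated exposure falls before the last dose; one mid-course ECG about 4 h post-dose would close this small gap

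*Protocol*

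**What the plan says.** **QT limit.** Protocol Section 3.3.4.3, item 5: "Dose escalation will be stopped if at least 2 subjects on active treatment at one dose level have relevant individual QT prolongations". A relevant prolongation is a QTc rise above 60 ms together with QT or QTc above 500 ms, confirmed on a repeat ECG.

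**Condition on in-group dosing.** Section 3.1 holds no formal review within a dose group, but "an individual will only be dosed in the absence of any safety concern (i.e. no dose-limiting events occurred) and if none of the" stopping criteria of Section 3.3.4.3 has been met. It adds that "an unscheduled safety review meeting can be requested anytime by the Principal Investigator (or an authorised deputy) or the sponsor of the study".

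**Risk mitigation.** Section 1.4.2.1.3 notes QT prolongation potential in monkeys. In the earlier multiple-dose trial, predicted mean QTcF differences from placebo at gMean Cmax,ss were below 10 ms at every dose, but "they slightly exceeded 5 msec in the 8 and 10 mg dose groups". Among its mitigations it states that "A dose escalation stopping criterion based on QT/QTc increase has been defined", and it promises frequent ECGs while relevant exposure is expected.

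**ECG schedule, Part I** (Flow Chart; SAP Table 6.7: 1).
- Day 1 dose: ECGs at 1, 2, 4, 8, 12, 24, 36 and 48 h. Flow Chart footnote 7 applies: "The ECG recording has to be performed in triplicate at this time". A single ECG follows at 96 h (Day 5).
- Days 6, 7, 9, 11, 13, 15 and 17: single ECGs at the nominal 09:00 dosing time. Sections 5.2.4.1 and 6.1 put the ECG first among activities sharing a time point.
- Day 12: intensive PK sampling, no ECG.
- Day 19: pre-dose ECGs at 431:15 to 431:45, then post-dose triplicates from 433:00, after the last dose at 432:00.

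**The concern.** Section 3.1 can protect subjects within a group only if the site sees relevant findings while a dose can still be withheld. The drug accumulates two- to more than threefold, and median tmax,ss is 4 to 5 h. A concentration-driven QT effect would therefore be largest some hours after a late daily dose. The only scheduled ECGs at such times either follow the first single dose, before accumulation, or follow the fifteenth and last dose. At stake is whether a marked individual prolongation at steady-state peak could be recognised during the 14 daily doses rather than only once they are over.

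**Working it through.** **Inputs.** Geometric means from Protocol Table 1.2.1: 2 (trial 1425-0002, same doses and regimen, capsules); ECG times from SAP Table 6.7: 1.

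**1. Check of the inputs.** Cmax,ss / Cmax should be close to the tabulated accumulation ratio RA_Cmax.

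| Dose (mg) | Cmax,ss / Cmax | Tabulated |
|---|---|---|
| 2 | 5.69/2.85 = 2.00 | 2.00 |
| 5 | 14.7/6.47 = 2.27 | 2.28 |
| 8 | 34.7/10.6 = 3.27 | 3.29 |
| 10 | 39.9/11.5 = 3.47 | 3.34 |

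The 10 mg difference fits 7 subjects at steady state against 8 after the first dose.

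**2. Time since the previous dose.** Daily doses are at 120, 144, ..., 432 h. The Day 6 ECG (120 h) precedes the first of them. Those at 144, 192, 240, 288, 336 and 384 h fall 24 h after the previous dose, and those at 431:15 to 431:45 fall 23.25 to 23.75 h after it. The first near-peak ECG under daily dosing is therefore in the series starting at 433:00, with 436:00 being 4 h after the last dose. The ±120 min window in Section 6.1 could let a dosing-time ECG slip to 2 h post-dose, still before median tmax,ss.

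**3. Exposure seen, as a fraction of Cmax,ss.**

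| Dose (mg) | Day 1 peak: Cmax / Cmax,ss | Pre-dose at steady state: C24,ss / Cmax,ss |
|---|---|---|
| 2 | 2.85/5.69 = 0.50 | 3.12/5.69 = 0.55 |
| 5 | 6.47/14.7 = 0.44 | 7.93/14.7 = 0.54 |
| 8 | 10.6/34.7 = 0.31 | 16.4/34.7 = 0.47 |
| 10 | 11.5/39.9 = 0.29 | 18.6/39.9 = 0.47 |

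Pre-dose fractions are lower before steady state.

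**4. What a pre-dose ECG would show.** Assumptions not in the documents: baseline QTc of 400 or 440 ms, effect proportional to concentration, no delay, and item 5 reached through QTc. The rise needed at peak is max(60, 500 − baseline).
- Baseline 400: 100 ms at peak. Pre-dose rise 100 × 0.466 to 100 × 0.548 = 47 to 55 ms (QTc 447 to 455 ms).
- Baseline 440: 60 ms at peak. Pre-dose rise 60 × 0.466 to 60 × 0.548 = 28 to 33 ms (QTc 468 to 473 ms).

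A subject who just reaches the limit at peak would show a visible change pre-dose, but below both parts of item 5. A delayed effect would narrow the gap.

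**5. What a mid-course ECG would see.** Approximate fraction of steady state after n daily doses, by two formulas in dose order 2, 5, 8, 10 mg:
- 1 − 2^(−24n/t1/2,ss), with t1/2,ss 74.4, 70.4, 46.8, 76.5 h. Day 12 (n = 7): 0.79, 0.81, 0.92, 0.78. Day 13 (n = 8): 0.83, 0.85, 0.94, 0.82.
- 1 − (1 − 1/RA_AUC)^n, with RA_AUC 2.30, 2.75, 3.69, 3.58. Day 12: 0.98, 0.96, 0.89, 0.90. Day 13: 0.99, 0.97, 0.92, 0.93.

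The range is 78% to 98% on Day 12 and 82% to 99% on Day 13. Both formulas assume mono-exponential accumulation, whereas the Protocol describes multiphasic decline. Seven daily doses (Days 13 to 19) could still be withheld after a Day 12 ECG, and six (Days 14 to 19) after a Day 13 ECG.

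**The case against.** The case for leaving the schedule alone is substantial, and most of it stands.

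- **Peak exposure of this size has been reached before.** In trial 1425-0001 (Table 1.2.1: 1), single 25 mg doses gave a gMean Cmax of 41.1 nmol/L in 6 subjects, against Cmax,ss of 39.9 nmol/L at 10 mg daily. Section 1.2.1 reports no clinically relevant change in any cardiac interval in any exposed subject.
- **Pre-dose ECGs are informative.** C24,ss exceeds single-dose Cmax at every dose (for example 18.6 against 11.5 nmol/L at 10 mg), and step 4 shows that a severe peak effect would leave a visible trace. Unscheduled ECGs (Section 5.2.4.1) and individual discontinuation (Section 3.3.4.1) are available.
- **Escalation has its own data.** Groups are at least 7 days apart, so the Day 19 to 21 triplicates are recorded before the next group starts. Before 10 mg, the 8 mg group has covered 34.7/39.9 = 87% of the expected peak; the step from 5 to 8 mg is larger (14.7/34.7 = 42%).
- **Continuous monitoring.** SAP Section 7.8.4 mentions continuous safety ECG monitoring by the investigator. The Flow Chart schedules none, so it cannot be counted on here.

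A reader might also infer that item 5 leaves in-group dosing unprotected, because it speaks only of escalation and counts active-arm subjects while "The treatments administered (active or placebo) will be blinded to the subjects and the investigators (outcome assessors"). The documents do not support this. Section 3.1 already bars dosing on any safety concern or met criterion, whatever the arm. Section 4.1.5.1 also says that "trial functions of the sponsor are unblinded (including Clinical Trial Leader"), so that role can make the count, and the sponsor can call a review. An arm-blind hold lifted because of a placebo subject could itself reveal allocation to the site.

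What remains is that the available warnings rely on judgement prompted by a signal at roughly half of peak exposure.

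**Conclusion.** The point holds as a minor scheduling improvement. While a daily dose can still be withheld, no subject in Part I has a scheduled ECG near tmax,ss at accumulated exposure. The last-dose ECGs supply that information too late for the subject's own dosing. This sits awkwardly with the mitigation promised in Section 1.4.2.1.3 and with the in-group condition in Section 3.1.

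The schedule gap follows directly from the documents. The 47% to 55% and 29% to 50% figures are ratios of geometric means from preliminary data in another trial, so individuals will vary. The QTc illustration rests on assumed baselines and on proportionality without delay.

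The likely benefit is small. Item 5 would need individual rises of at least 60 ms, while predicted mean differences were below 10 ms and no relevant individual change was seen. The finding does not show that escalation is unsafe or that the stopping rule is unusable, and item 5 needs no rewording on this ground.

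**What to change.** Schedule one 12-lead ECG about 4 h post-dose in mid-course, read by the site before the next dose. A single ECG is enough, since item 5 already asks for a confirming repeat. State a narrow window, such as the ±15 min that Section 6.1 uses early after dosing; ±120 min would allow 2 to 6 h. There are two ways to do it:

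1. **Re-time the Day 13 ECG** from 288:00 to 292:00. No procedure is added. One pre-dose ECG is lost, and the neighbouring gaps become 292 − 240 = 52 h and 336 − 292 = 44 h, against 48 h each now.
2. **Add an ECG on Day 12** at 268:00, when PK blood is already drawn. This costs 48 single ECGs (one per Part I subject), keeps all pre-dose ECGs and leaves one more dose that can be withheld.

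Subjects are in-house on both days. Neither option needs an extra blood sample or central reading. The Flow Chart and SAP Table 6.7: 1 would each change by one row.
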